# Intervention

All children were hospitalized for 2 weeks and received conventional exercise therapy including range of motion, strengthening, trunk control and strengthening exercises and exercises to improve fine and gross motor skills during hospital inpatient stay throughout 2 weeks 2 hours a day (SG). Control group received conventional exercise therapy only. SPIO 2 hours group received conventional exercise therapy with the garment on for 2 hours. SPIO 6 hours group wore the SPIO 4 hours more in addition to 2 hours during therapy. After the treatment for two weeks, during the follow-up period SPIO groups continued wearing the orthosis at home and all the children continued their regular therapies for one hour a day, two days a week. After hospitalization, wear time of garment during follow-up was checked by weekly phone calls. No other changes in physiotherapy or orthotic management or no addition of a new treatment method were permitted during follow-up.

#### **Outcome measures**

The primary outcomes of interest were feasibility and evaluating posture and balance during sitting, therefore SAS was set as the primary outcome measure while secondary outcome measures were Gross Motor Function Measure (GMFM), Box and Block Test (BBT), Parent Satisfaction Survey.

Assessments were conducted before treatment (BT) (TO), at posttreatment (PT), 1 month posttreatment (1 MPT) and 3 months posttreatment (3 MPT) (EG). SAS and BBT were also tested immediately after the orthosis was worn (EG). Children were assessed without the suit on and without any other orthosis except for the assessment of the immediate effect. During the assessment of the immediate effect children wore SPIO under their clothings to hide orthosis from the evaluator.

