## Study design

The study was designed as prospective, single-blinded, randomized, controlled trial. Children with CP were randomized to either of three groups: SPIO 2 hours, SPIO 6 hours and control group (EKS) which the assessors were blinded to (EG, TO). To ensure group concealment, randomization was done using sealed opaque envelopes which were sequencly numbered in

advance, including the information about which group the child would have been allocated to. The physiotherapist opened the envelopes and started the interventions according to group allocation.

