# Sample size

It was found out that 8 individuals for each group must had been recruited to have 80% power with 5% type 1 error level to detect a minimum clinically significant difference of 1 units of Sitting Assessment Scale score, when the average expected value in the first group was 16.47, with a standard deviation of 1.96 and the average expected value in the second group was 13.20, with a standard deviation of 3.32 based on the previous research conducted by Şimşek et al evaluating the effects of kinesiology taping on trunk control .

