# Sitting Assessment Scale (SAS)

Sitting Assessment Scale (SAS) was used to evaluate posture and balance during sitting while sitting dimension of Gross Motor Function Measure (GMFM) were used for assessing sitting as a gross motor function. Box and Block Test was used to evaluate gross manual dexterity. Sitting Assessment Scale was developed for observational assessment of posture and balance during sitting after seating interventions. The scale consists of 5 items including head control, trunk control, foot control, arm function and hand function which are assessed as follows: 1 = none; 2 = poor; 3 = fair; 4 = good). The minimum and maximum possible scores are 5 to 20 respectively. SAS has high intra (ICC 0,87-1,0) and inter rater reliability (ICC 0,87-1,0)  $^{17,18}$ .

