# Gross Motor Function Measure-B, sitting dimension

Gross Motor Function Measure shows gross motor functional status and changes in functional status of children ages between 15 months and 13 years after interventions. It is composed of 88 items which are categorized into 5 dimensions including lying and rolling (17); sitting (20); crawling and kneeling (14); standing (13); and walking, running, and jumping (24). It

assesses degree of achievement of gross motor functions rather than quality of them. Each item is scored according to special instructions on GMFM Manuel with a 4-point Likert scale including 0 = does not initiate, 1 = initiates, 2 = partially completes, 3 = completes. If it is not possible to test an item, it should be noted as not tested (NT) . The reliability of GMFM has been found to be excellent (ICC= 0.99 for total score; ICC= 0.98 for sitting dimension) . In this study sitting dimension of GMFM was used to evaluate degree of achievement of sitting as a gross motor function. Evaluations were done according to GMFM User's Manuel .

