3.03.2017

The Effect of Vest Type Dynamic Elastomeric Fabric Orthosis (DEFO) on Sitting Balance and Gross Manual Dexterity in Children With Bilateral Cerebral Palsy: A Feasibility and Randomized, Single-blinded, Pilot Study (NCT03191552)

(Unique Protocol ID:09.2013.0351)

STATISTICAL PLAN

IBM SPSS Statistics for Windows, Version 20,0 (Armonk, NY, USA) will be used to perform all of the analysis. Statistical significance is accepted as $p < 0.05$. Descriptive statistics will be used to determine mean \pm SD of data. Chi-square and t-tests will be used to compare demographic findings. The histogram and normality plots and Shapiro-Wilk normality test were used for data distribution analysis. Between group analysis will be performed using ANOVA if data followed normal distribution. But if not Kruskal-Wallis test will be performed. Mann-Whitney U test was performed to test the significance of pairwise differences using Bonferroni correction (post-hoc test) to adjust for multiple comparisons. For Bonferroni correction, a p value of less than 0.017 ($0.05/3$) was determined as the level of statistical significance

Depending on the distribution analysis, Wilcoxon and dependent t-test will be utilized to detect within group analyzes. To assume changes over time with treatment Friedman and repeated measures analysis of variance will be conducted.

Mann Whitney u and independent sample t-tests will be applied to compare SPIO 2 hours and 6 hours group. To compare groups in pairs in terms of parent satisfaction questionnaire results chi square test will be done.

To evaluate feasibility, recruitment and retention rates will be calculated and percentages will be reported.

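### Baseline and later visits were scored by different assessors, so within-arm tests of SAS change from baseline cannot separate change in the children from a switch of rater

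*Protocol*

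**What the plan says.** The Protocol's Study design section identifies two blinded assessors by code: "control group (EKS) which the assessors were blinded to (EG, TO". The Outcome measures section then assigns visits to them: "Assessments were conducted before treatment (BT) (TO), at posttreatment (PT), 1 month posttreatment (1 MPT) and 3 months posttreatment (3 MPT) (EG". One code follows baseline and the other closes the list of the three later visits. The garment-on test carries the second code as well: "SAS and BBT were also tested immediately after the orthosis was worn (EG". The score it is compared with is not named.

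SAS is the primary outcome. The Protocol describes it as an observational scale of five items, with totals from 5 to 20. On reliability it cites "SAS has high intra (ICC 0,87-1,0) and inter rater reliability (ICC 0,87-1,0", taken from earlier sources, without the type of coefficient and without data on these two assessors.

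The SAP says "Wilcoxon and dependent t-test will be utilized to detect within group analyzes", and adds Friedman or repeated-measures ANOVA for the time course. Between-group comparisons use ANOVA or Kruskal-Wallis. Neither document mentions rater training, double scoring, an agreement check in this study, or a rater term.

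**The concern.** For any contrast with baseline, visit and rater change together. The observed change is the true change plus the difference in scoring level between the two assessors, and the planned data cannot split that sum. A more lenient later assessor could make an arm appear to improve when the children have not changed. A stricter one could hide a real gain.

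This affects the paired t-test, the Wilcoxon test, Friedman's test and the time effect in a repeated-measures ANOVA whenever baseline is included. It also affects the immediate garment effect if baseline is its reference. The SAP sets p < 0.05 for its analyses and does not call the within-arm ones descriptive. A statement that an arm improved on the primary outcome could therefore be a rater effect.

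**Working it through.** **The plan's own figure.** The only computed design figure is 8 per group, and this point does not rest on it. With a difference of 16.47 − 13.20 = 3.27 and pooled SD 2.73, the normal approximation n = 2(z_α + z_β)²SD²/Δ² gives 9 per group one-sided and 11 two-sided at 5% and 80% power. Only n = 8 and the SDs are used below. The plan gives no rater offset and no SD of SAS change.

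**Who scored what.**

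| Assessment | Natural reading | Narrowest reading (second code covers 3 months only) |
|---|---|---|
| Baseline | first assessor | first assessor |
| Garment-on test | second | second |
| Post-treatment, 1 month | second | not stated |
| 3 months | second | second |

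On either reading, baseline to 3 months crosses raters, and so does baseline to the garment-on test.

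**How large an offset the cited reliability allows.**
- Pooled variance from the Sample size section: (1.96² + 3.32²)/2 = 7.43, SD 2.73.
- Suppose 0.87 is an absolute-agreement coefficient and 7.43 is total variance. Variance not due to the children is then 0.13 × 7.43 = 0.966.
- If all of that is systematic, two raters differing by b contribute b²/2, so b = √(2 × 0.966) = 1.39 points.
- At a coefficient of 1.0, the top of the cited range, b = 0.
- A consistency coefficient ignores a constant offset and sets no bound.

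The upper figure exceeds the Protocol's own benchmark, which is "to detect a minimum clinically significant difference of 1 units of Sitting Assessment Scale score".

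**What an offset does to a within-arm test.** Take n = 8, no true change, two-sided 5%, 7 degrees of freedom. The paired t statistic is noncentral t with noncentrality b√8/SD, where SD is the SD of change. For b = 1 this is 2.83 at SD 1.0 and 1.13 at SD 2.5. Chance of a significant result:

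| Assumed SD of change | Offset 0 | Offset 0.5 | Offset 1.0 |
|---|---|---|---|
| 1.0 | 5% | 23% | 68% |
| 1.5 | 5% | 13% | 37% |
| 2.0 | 5% | 9% | 23% |
| 2.5 | 5% | 8% | 17% |

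The SDs are assumptions, but both ends can be placed.
- Lower end: with total variance 7.43, absolute agreement 0.87 and a 1-point offset, the offset uses 1²/2 = 0.5 of the 0.966. Random error alone then gives an SD of change of √(2 × 0.466) = 0.97.
- Upper end: an assumed visit-to-visit correlation of 0.6 gives 2.73 × √(2 × 0.4) = 2.44.

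By simulation, the exact Wilcoxon test with a 1-point offset rejects about 31% of the time at SD 1.5 and 20% at SD 2.0, against about 3.5% with no offset.

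**What an offset does to between-group tests.** If every arm has the same offset b, the difference in mean change is (true change A + b) − (true change B + b), and b cancels. In a same-visit comparison b shifts all arms equally. In ANCOVA it goes into the intercept. A simulated between-arm t-test of change with a 1-point offset in both arms rejected 4.8% to 5.0% of the time.

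**The case against.** The strongest reply is that little of importance rests on these tests. Every arm received two weeks of inpatient therapy at 2 hours a day, so within-arm change could not show a garment effect even with one rater. The study is a pilot, and the randomised comparison is unaffected by a common offset. The SAP does not say that its repeated-measures ANOVA is run arm by arm; if group is included, the group-by-time interaction is also unaffected. Cited reliability for SAS is high, a separate follow-up assessor avoids recall of baseline scores, and calibration that is not described may still have taken place.

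Most of this stands, and it limits the point to contrasts with baseline that lack a comparison between arms. It does not remove the problem, because the SAP plans those tests at a significance threshold and nothing in either document allows the offset to be estimated.

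A reader might infer more than the documents support:
- **That the efficacy comparison is biased.** Assessors are assigned by visit, not by arm, and are described as blinded. Nothing suggests an offset that differs between arms.
- **That the two assessors do differ.** The 1.4-point figure is what a coefficient of 0.87 would permit under stated assumptions. It is not an estimate.
- **That a false improvement in at least one of the three arms is likely.** Such a figure needs zero true change in three actively treated arms.
- **That the garment-on session unblinded the second assessor.** The Protocol says "During the assessment of the immediate effect children wore SPIO under their clothings to hide orthosis from the evaluator", and does not say whether controls had a matching session.

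**Conclusion.** The concern holds for tests within an arm, or of the main effect of time, that include baseline. It is mainly about SAS. The Box and Block Test is a count, and for the sitting dimension of the Gross Motor Function Measure the Protocol cites "The reliability of GMFM has been found to be excellent (ICC= 0.99 for total score; ICC= 0.98 for sitting dimension", so both are probably less affected. On the natural reading, comparisons among post-treatment, 1 month and 3 months share one rater.

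The offset has unknown size and direction and may be zero. Under absolute agreement at 0.87, with 7.43 as total variance, it could reach about 1.4 points. The 17% to 68% for a 1-point offset is an illustration that depends on assumed SDs of change of 1.0 to 2.5, n = 8 and no true change.

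Same-visit comparisons, change-score comparisons and any group-by-time interaction remain usable, provided the offset is common to all arms. The immediate effect shares the problem only if baseline is its reference. This should be fixed, but it does not undermine the trial.

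**What to change.** In the SAP:
- Base efficacy conclusions on between-group contrasts at post-treatment, 1 month and 3 months, adjusted for the baseline score already collected, for example by ANCOVA. Unadjusted same-visit comparisons are equally free of a common offset; adjustment also deals with chance baseline imbalance at 8 per arm.
- Label within-arm change from baseline as descriptive and confounded with rater. Do the same for the immediate effect if baseline is its reference.

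In the Protocol's Outcome measures section:
- State who scored each visit.
- State what the garment-on score is compared with.

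The cost is text and one model on existing data. The downside is that within-arm p-values from baseline can no longer support a claim that an arm improved. Baseline need not be removed from the over-time tests: doing so would lose the treatment period, and the label is enough.

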# Sitting Assessment Scale (SAS)

Sitting Assessment Scale (SAS) was used to evaluate posture and balance during sitting while sitting dimension of Gross Motor Function Measure (GMFM) were used for assessing sitting as a gross motor function. Box and Block Test was used to evaluate gross manual dexterity. Sitting Assessment Scale was developed for observational assessment of posture and balance during sitting after seating interventions. The scale consists of 5 items including head control, trunk control, foot control, arm function and hand function which are assessed as follows: 1 = none; 2 = poor; 3 = fair; 4 = good). The minimum and maximum possible scores are 5 to 20 respectively. SAS has high intra (ICC 0,87-1,0) and inter rater reliability (ICC 0,87-1,0)  $^{17,18}$ .

# Gross Motor Function Measure-B, sitting dimension

Gross Motor Function Measure shows gross motor functional status and changes in functional status of children ages between 15 months and 13 years after interventions. It is composed of 88 items which are categorized into 5 dimensions including lying and rolling (17); sitting (20); crawling and kneeling (14); standing (13); and walking, running, and jumping (24). It

assesses degree of achievement of gross motor functions rather than quality of them. Each item is scored according to special instructions on GMFM Manuel with a 4-point Likert scale including 0 = does not initiate, 1 = initiates, 2 = partially completes, 3 = completes. If it is not possible to test an item, it should be noted as not tested (NT) . The reliability of GMFM has been found to be excellent (ICC= 0.99 for total score; ICC= 0.98 for sitting dimension) . In this study sitting dimension of GMFM was used to evaluate degree of achievement of sitting as a gross motor function. Evaluations were done according to GMFM User's Manuel .

# **Box and Block Test**

Box and Block Test which consists of a box divided into two compartments by a partition and blocks with standardized dimensions is used to assess unilateral gross manual dexterity. The object is instructed to transport boxes one by one from one compartment of the box to other in 60 seconds. The score is the number of boxes transferred from one compartment to other in 60 seconds. The object should sit on a chair with a standard height and face the box. He/she should practice for a 15 second trial period before testing. If two blocks are carried at the same time, it is counted as one. And also if the block falls on the floor after it has been carried across, it is still counted .

## **Parent Satisfaction Survey**

A non-standardized 5-point Likert type scale was invented by the investigators to assess compliance and satisfaction with wearing orthosis. Parents were completed the questionnaire PT, 1 MPT and 3 MPT. The items numbered 3, 5 and 7 were questioning about treatment efficiacy while the other items were questioning the ease and utilization of the use of orthosis. That's why to compare all groups only 3.,5. and 7. items were used when all of them were completed for the comparisons of SPIO groups.

3.03.2017

The Effect of Vest Type Dynamic Elastomeric Fabric Orthosis (DEFO) on Sitting Balance and Gross Manual Dexterity in Children With Bilateral Cerebral Palsy: A Feasibility and Randomized, Single-blinded, Pilot Study (NCT03191552)

(Unique Protocol ID:09.2013.0351)

STATISTICAL PLAN

IBM SPSS Statistics for Windows, Version 20,0 (Armonk, NY, USA) will be used to perform all of the analysis. Statistical significance is accepted as $p < 0.05$. Descriptive statistics will be used to determine mean \pm SD of data. Chi-square and t-tests will be used to compare demographic findings. The histogram and normality plots and Shapiro-Wilk normality test were used for data distribution analysis. Between group analysis will be performed using ANOVA if data followed normal distribution. But if not Kruskal-Wallis test will be performed. Mann-Whitney U test was performed to test the significance of pairwise differences using Bonferroni correction (post-hoc test) to adjust for multiple comparisons. For Bonferroni correction, a p value of less than 0.017 ($0.05/3$) was determined as the level of statistical significance

Depending on the distribution analysis, Wilcoxon and dependent t-test will be utilized to detect within group analyzes. To assume changes over time with treatment Friedman and repeated measures analysis of variance will be conducted.

Mann Whitney u and independent sample t-tests will be applied to compare SPIO 2 hours and 6 hours group. To compare groups in pairs in terms of parent satisfaction questionnaire results chi square test will be done.

To evaluate feasibility, recruitment and retention rates will be calculated and percentages will be reported.

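### The between-group SAS analysis names no baseline adjustment and does not say whether score or change is compared, a likely loss of precision with 8 children per arm

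*SAP*

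**What the plan says.** Under Outcome measures, the Protocol states of the Sitting Assessment Scale: "therefore SAS was set as the primary outcome measure". The same section schedules it before treatment, at post-treatment (PT), and at 1 and 3 months post-treatment (1 MPT, 3 MPT), so every child should have a baseline value.

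The SAP's Statistical Plan sets out the group comparisons in three places:

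- Overall: "Between group analysis will be performed using ANOVA if data followed normal distribution. But if not Kruskal-Wallis test will be performed".
- Pairs, at 0.05/3 = 0.017: "Mann-Whitney U test was performed to test the significance of pairwise differences using Bonferroni correction (post-hoc test) to adjust for multiple comparisons".
- The two garment arms: "Mann Whitney u and independent sample t-tests will be applied to compare SPIO 2 hours and 6 hours group".

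Time enters through within-group tests (Wilcoxon or dependent t) and through this sentence: "To assume changes over time with treatment Friedman and repeated measures analysis of variance will be conducted". No group factor or group-by-time term is mentioned there.

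None of these names the before-treatment SAS as a covariate. None says whether the variable compared is the later score or its change from before treatment.

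**The concern.** Two separate things are missing.

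**The analysis variable.** A test of later scores and a test of change scores are different analyses with different precision. Which is better depends on r, the correlation between before-treatment and later SAS. The documents do not give r, so a reader cannot tell which analysis is intended or how precise it would be. The choice could also be made after seeing the data.

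**Use of the baseline.** With 8 children per arm, chance imbalance is common. If baseline SAS has the SD of 2.73 assumed below, the difference between two arm means has SD 2.726 × √(2/8) = 1.363. Two arms then differ by more than 1 point at baseline with probability about 46%. One point is what the Protocol's Sample size section calls "a minimum clinically significant difference of 1 units of Sitting Assessment Scale score". Randomisation means this is not bias, but an unadjusted comparison of later scores leaves the predictable part of that imbalance in the error. The interval around the garment effect is then wider than it need be whenever r is more than small.

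**Working it through.** **Inputs (Protocol, Sample size).** Means 16.47 and 13.20, difference 3.27; SDs 1.96 and 3.32; 8 per group; 80% power; 5% type I error, sidedness not stated. Three arms (Study design). Pairwise alpha 0.05/3 (SAP). Assumed: r = 0 to 0.8; a common SD at baseline and follow-up; approximately normal data.

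**Pooled SD.** √((1.96² + 3.32²)/2) = 2.726.

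**The plan's own figure.** n = 2 × (2.726 × (z₁₋α + z₀.₈)/3.27)² gives 8.6, so 9 per group, with a one-sided 5% test. It gives 10.9, so 11, two-sided. The stated 8 is approached only one-sided and on the 3.27 difference. That is a separate matter; the present point does not rest on it.

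**Standard error of one garment arm against control, 3 × 8 children, pooled error:**

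- Later score: SE = 2.726 × √(2/8) = 1.363, 21 df.
- Change: SD = 2.726 × √(2(1−r)), same 2/8 factor, 21 df.
- ANCOVA: residual SD = 2.726 × √(1−r²), 20 df. The 2/8 factor is inflated for chance baseline imbalance by 1 + 1/19 on average.

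**Worked case, r = 0.5.** Change has SD 2.726 × √1, so its SE is also 1.363. ANCOVA has 2.726 × √0.75 = 2.361, and SE ≈ 2.361 × √(0.25 × 20/19) = 1.211. The unadjusted SE is larger by 1.363/1.211 = 1.125, about 13%.

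**Power from the noncentral t, two-sided (ANCOVA averaged over simulated baselines):**

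| Difference, alpha | Analysis | r=0 | 0.3 | 0.5 | 0.7 | 0.8 |
|---|---|---|---|---|---|---|
| 3.27, 0.05 | Score | 63% | 63% | 63% | 63% | 63% |
| | Change | 37% | 49% | 63% | 84% | 95% |
| | ANCOVA | 61% | 65% | 73% | 88% | 96% |
| 3.27, 0.05/3 | Score | 44% | 44% | 44% | 44% | 44% |
| | Change | 21% | 31% | 44% | 69% | 87% |
| | ANCOVA | 41% | 45% | 55% | 74% | 89% |
| 1, 0.05 | Score | 11% | 11% | 11% | 11% | 11% |
| | Change | 8% | 9% | 11% | 15% | 20% |
| | ANCOVA | 10% | 11% | 12% | 16% | 21% |

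**Mean half-width of the 98.3% interval (level 1 − 0.05/3), in SAS points:**

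| Analysis | r=0 | 0.3 | 0.5 | 0.7 | 0.8 |
|---|---|---|---|---|---|
| Score | 3.50 | 3.50 | 3.50 | 3.50 | 3.50 |
| Change | 4.96 | 4.15 | 3.50 | 2.71 | 2.22 |
| ANCOVA | 3.61 | 3.44 | 3.12 | 2.58 | 2.16 |

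**Break-even points.** Score and change are equal when 2(1−r) = 1, so r = 0.5. ANCOVA and score have equal variance when (1−r²)(20/19) = 1, so r = √0.05 = 0.22. Allowing for the lost degree of freedom, power is equal at r of about 0.23.

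**Check on a bounded scale.** Scores were rounded and limited to 5 to 20, with two arms of 8 and alpha 0.05. With no true difference, type I error was 0.049 to 0.051 for ANCOVA and 0.049 to 0.052 for rank ANCOVA. At 3.27, the t-test on scores had power 0.60 to 0.61. At r = 0.5 and 0.7, ANCOVA had 0.69 and 0.84, and rank ANCOVA 0.67 and 0.79.

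**The case against.** The omissions and the arithmetic are not in dispute. The case against concerns weight.

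- **It is an efficiency choice in a feasibility pilot.** The planned tests are valid. At the Protocol's 1-unit difference, power at 0.05 moves only from 11% to between 10% and 21%. This stands: no hypothesis test is rescued, and the benefit is the interval.
- **No r is documented.** Eligibility limited to GMFCS and MACS levels III-IV, and different raters before treatment and later, could lower r. The inter-rater ICC of 0.87 to 1.0 quoted in the Protocol limits the second point. This also stands, so the loss can be called likely but not given one figure.
- **Against change scores the gain is small when r is high.** At 0.05/3 it is 74% against 69% at r = 0.7, and 89% against 87% at r = 0.8. That is true, but the SAP does not say that change is what will be compared.
- **Repeated-measures ANOVA may already use the baseline.** Take the mean of PT, 1 MPT and 3 MPT minus before treatment, with all correlations equal to r and an effect constant over visits. At 0.05/3 its power is 47, 63, 87 and 97% for r = 0.3, 0.5, 0.7 and 0.8, above ANCOVA of a single visit. This is the strongest objection. However, that contrast answers a different question and needs a sustained effect. The SAP states neither the group factor nor the interaction that it requires, and Friedman's test has no group factor.
- **The benchmark is not the planned pairwise test.** A two-arm Mann-Whitney test on bounded scores has power of about 35% at 0.05/3 and 58% at 0.05. This favours adjustment.

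**Conclusion.** The concern holds as a point about precision and pre-specification, not bias. The SAP neither defines the SAS variable compared between groups nor uses the before-treatment value already scheduled.

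Its size depends on r. Relative to a test of later scores, ANCOVA shortens the 98.3% half-width by about 11% at r = 0.5 (3.12/3.50) and 26% at r = 0.7 (2.58/3.50). It gains little at r = 0.3 and costs about 2 power points at r = 0. Relative to change scores, its advantage is large at low r and small from 0.7 upwards. The score-or-change choice alone moves power at 0.05/3 between 44% and 21% at r = 0, and between 44% and 87% at r = 0.8.

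These figures rest on a common SD of 2.73, although the Protocol's two SDs are 1.96 and 3.32; on near-normal scores; and on 8 analysed children per arm. The change should be made, but the trial's validity does not depend on it.

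**What to change.** In the SAP's Statistical Plan:

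1. State the variable and the visit for the primary between-group SAS comparison, for example the score at PT.
2. Make that analysis an ANCOVA of the score on group with before-treatment SAS as covariate. Report adjusted pairwise differences with confidence intervals at the 0.05/3 level already chosen.
3. Because SAS is a bounded sum of ordinal items, pre-specify a rank ANCOVA or a permutation test of the same contrast as a sensitivity analysis. It should not be a fallback selected by a normality test.
4. If repeated-measures ANOVA is kept for PT, 1 MPT and 3 MPT, include group and group-by-time, and label the within-group tests descriptive.

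The cost is wording, with no new data collection. ANCOVA uses one degree of freedom, assumes approximate linearity in baseline SAS with a common slope across arms, and loses about 2 power points if r is near zero. If outcomes have already been examined when the change is made, the adjusted analysis should be labelled as added afterwards.

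### The SAP lets loosely defined normality checks on about 8 children per arm choose the SAS test. One fixed, baseline-adjusted model would be a cheap improvement.

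*SAP*

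**What the plan says.** The SAP gives one between-group rule for all outcomes: "Between group analysis will be performed using ANOVA if data followed normal distribution", and Kruskal-Wallis if they do not. The distribution is judged from a histogram, normality plots and a formal test ("Shapiro-Wilk normality test were used for data distribution analysis"). The same kind of switch governs the within-group tests.

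The SAP does not state:
- a cut-off for Shapiro-Wilk in this role;
- what happens when plots and test disagree;
- whether the check is made per arm, on pooled data or on residuals;
- whether it is made once per outcome or separately at each visit.

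The protocol (Outcome measures) makes the Sitting Assessment Scale (SAS) the primary measure. SAS is assessed before treatment, after treatment, and at 1 and 3 months, with an additional immediate test. On the scale itself: "The minimum and maximum possible scores are 5 to 20 respectively". It is the sum of five items scored 1 to 4, so scores are whole numbers. Under Sample size, "8 individuals for each group must had been recruited" for "80% power with 5% type 1 error level". Neither document fixes the SAS test in advance or uses baseline SAS in the between-group comparison.

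**The concern.** A preliminary normality test is least informative in a small sample. With about 8 whole-number scores per arm it will usually miss real skew, and it can reject merely because rounding produces ties. Two of the three criteria are visual, so two analysts could reach different branches from the same data.

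At stake is whether a reader can know beforehand which test will produce the SAS result, and whether the post-treatment visits share one test and one effect measure. The rule also spends its effort choosing between two unadjusted tests, although a baseline SAS score that could sharpen the comparison is already collected.

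**Working it through.** **Inputs.** From the protocol: three arms of 8; whole-number SAS from 5 to 20; planning means of 16.47 (SD 1.96) and 13.20 (SD 3.32), given under Sample size. Assumed, because the documents do not say: Shapiro-Wilk at 0.05; any rejection leads to Kruskal-Wallis; two arms at 16.47 (SD 1.96) and one at 13.20 (SD 3.32); normal scores rounded and capped to 5–20; within-child correlation 0.7 where visits are combined.

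**The plan's own figure.** The difference is 16.47 − 13.20 = 3.27, and the SD is √((1.96² + 3.32²)/2) = 2.73. The two-sided normal formula gives n = 2(1.96 + 0.84)² × 2.73²/3.27² ≈ 11 per arm (12 by t), not 8. One-sided it gives 9. The stated 8 is not reproduced. That is a separate matter, and the point here does not depend on it.

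**Can the check do its job at n = 8?**
- Exponential data: rejected in about 33–34% of samples.
- Gamma data with shape 2: about 18–19%.
- Normal scores rounded to SAS integers: 11% (SD 1.96) and 7% (SD 3.32).
- Three per-arm checks on truly normal data: 1 − 0.95³ = 14%, and about 15% in simulation. With SAS-like scores, 22–27%.

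**How often does the switch change the verdict?** At the planning values (20,000 runs, SAS-like scores) power is 67.7% for ANOVA, 57.0% for Kruskal-Wallis and 65.1% for the rule. The two tests fall on opposite sides of 0.05 in 11.8% of trials (8.4% if the third arm lies midway). The verdict departs from a fixed ANOVA only when the tests disagree and the check also triggers the switch. Treating these as roughly independent:
- per-arm checks: 0.118 × 0.274 = 0.032;
- residual checks: 0.118 × 0.084 = 0.010.

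Direct simulation gives about 3% and 1%. With no effect, the figures are about 0.5% and 0.2%.

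**Type I error.** The mechanical per-arm rule gives 4.9–5.3% across normal, SAS-like and skewed data. Always taking the more favourable of the two tests gives 5.5–6.1%.

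**Mixing across the three post-treatment visits**, if the choice is made visit by visit: about 46–58% of trials with per-arm checks and 14–24% with residual checks, across scenarios. With per-arm checks and SAS-like scores at the planning values, correlations of 0.5 and 0.8 give 58% and 56%. The result depends far more on the unit of the check than on the correlation.

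**What baseline adjustment offers.** A covariate with correlation ρ to the outcome leaves a residual variance of about (1 − ρ²) of the original, so 8 per arm acts like roughly 8/(1 − ρ²), ignoring one degree of freedom:
- ρ = 0.5: 8/0.75 = 10.7;
- ρ = 0.7: 8/0.51 = 15.7;
- ρ = 0.8: 8/0.36 = 22.2.

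At ρ = 0.7, simulated power rises from about 67% to 89%.

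**The case against.** The strongest reply is that the SAP names both tests and the branching condition in advance, and that the rule applied mechanically is nearly harmless. This stands. A reader might infer that the false-positive rate is inflated; the simulations do not show that.

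A reader might also infer that the SAS verdict hangs on a near-random switch, taking the roughly 12% disagreement as its effect. That figure applies only if both tests are run and one is picked freely. The written rule departs from ANOVA in about 1–3% of trials. The part of the concern that survives is discretion: two of the three criteria are read by eye, so the 1–3% is not guaranteed. How far discretion would move it towards 12% cannot be quantified from the documents.

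A third tempting reading is that most trials would test SAS differently at different visits. That needs per-arm checks and a separate choice at each visit. The SAP specifies neither, and one choice for the whole outcome is equally compatible with its text.

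Finally, this is a feasibility pilot, and recruitment and retention percentages are unaffected. But the protocol sizes the study for power on SAS and the SAP tests at 0.05, so the pilot label does not remove the point.

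**Conclusion.** The point holds as a cheap improvement, not as a threat to validity. The SAS test is left to checks that have little power at this size and are incompletely specified. Applied mechanically, the cost is small: type I error near 5%, and a verdict different from fixed ANOVA in about 1–3% of trials at the planning values. Discretion over plots could raise the latter towards roughly 12%.

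Mixed tests over the post-treatment visits could occur in anything from about 14% to 58% of trials, depending mainly on a check unit that the SAP leaves open. These figures rest on the assumed 0.05 cut-off, the assumed score shapes and, for mixing, a correlation of 0.7.

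The larger gain comes from using baseline SAS. Its size depends on a baseline-outcome correlation that the documents do not give.

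**What to change.** In the SAP, delete the normality-driven switch for SAS. Name one analysis for every post-treatment visit: a linear model of SAS on arm with before-treatment SAS as covariate. State that Kruskal-Wallis will always be reported as a sensitivity analysis, whatever the data look like.

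The cost is about two sentences. No extra children, visits or measurements are needed, because baseline SAS is already collected.

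The downside is that the model treats an ordinal sum score with a ceiling at 20 as continuous in small arms; the rank analysis would show whether that matters. Naming either existing test would also remove the open choice, but would forgo the gain from baseline. The change does not settle which visit is primary. Neither document says, and that needs its own sentence.
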